
Study Schedule/Procedures: During screening and every 21 days from the date of first study drug administration (Day 1), a study visit will be conducted that includes a physical examination, clinical laboratory tests, and an assessment of AEs. [REDACTED]
 
[REDACTED]
 
During screening, subjects will have an objective assessment of disease status performed by fluorodeoxyglucose (FDG) positron emission tomography (PET) and diagnostic quality CT scan or MRI. Subjects will also have a bone marrow biopsy performed at screening unless the subject has FDG-avid disease or has undergone a recent bone marrow biopsy. Disease status will be subsequently assessed by PET-CT/MRI at Weeks 9, 18, 27, and every 18 weeks thereafter until disease progression. On-study bone marrow biopsies will be required only if needed to confirm a CR/CMR.
 
Subjects withdrawn from study treatment for reasons other than disease progression will be followed for disease assessment until either radiologic disease progression, the start of a new anticancer therapy, or death (whichever occurs first).
 
Subjects withdrawn from study treatment because of disease progression will be followed approximately every 12 weeks for subsequent anticancer therapies and survival.
 
Note: With Amendment 4, Protocol-required procedures have been reduced for ongoing subjects.

Estimated Duration of Participation: Subject participation through safety follow-up is expected to average approximately 11 months, which includes the following:
 

• A screening period lasting up to 28 days.

• A treatment period lasting as long as the subject is receiving benefit, tolerating the regimen, and has not met withdrawal criteria (approximately 9 months).

• A safety follow-up period lasting 30 to 35 days.

 
Subjects will be followed for approximately 12 months after the safety follow-up period.

Estimated Number of Subjects: The target enrollment for this study is 100 to 120 subjects.

Principal Coordinating Investigator: [REDACTED], MD, [REDACTED]

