#### 1.4. Study Rationale

Aberrant activation of PI3K $\delta$  has been associated with increased malignant B-cell proliferation and survival. Another PI3K $\delta$  inhibitor, idelalisib, received approval from the FDA for the treatment of patients with relapsed CLL, in combination with rituximab, and also received accelerated approval from the FDA for the treatment of patients with relapsed follicular B-cell non-Hodgkin lymphoma (FL) or relapsed small lymphocytic lymphoma. Idelalisib was also approved by the European Medicines Agency for patients with chronic CLL who have received at least 1 prior therapy or in certain first-line settings and for FL that is refractory to at least 2 lines of treatment. The approvals were based on objective response rate (ORR) and demonstrate that inhibition of PI3K $\delta$  can be an effective strategy in the treatment of some B-cell malignancies.

INCB050465 is a potent and selective inhibitor of PI3K $\delta$  in enzyme and B-cell proliferation assays. Based on emerging safety, efficacy, [REDACTED] data from the ongoing Study INCB 50465-101 (see Section 1.3), subjects with relapsed or refractory DLBCL who have received 2 to 5 prior regimens and who are ineligible for HDC/ASCT will receive INCB050465 administered orally at a dose of 20 mg QD for 8 weeks followed by 20 mg once weekly. This dose was chosen based on emerging efficacy and safety data from the ongoing Study INCB 50465-101 (see Section 1.3). [REDACTED]

Furthermore, 20 mg QD has demonstrated efficacy in DLBCL (2 CMRs in 2 subjects) and in other types of non-Hodgkin lymphomas (9 objective responses in 9 subjects with non-Hodgkin lymphoma). However, 24% (n = 11) of all subjects in study INCB 50465-101 discontinued study treatment due to an AE. All but 1 of these events occurred after the 9-week disease assessment. Among the subjects with an objective response (n = 20), 7 (35%) discontinued study treatment due to an AE. Consequently, after administration of 20 mg QD for 8 weeks, the dosing regimen will be reduced to 20 mg once weekly. This once-weekly regimen is proposed to maintain response while providing time off from pathway inhibition, which may reduce the frequency of AEs. [REDACTED]

[REDACTED] This once-weekly regimen is similar to

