6.4. Exposure

For subjects in the safety population, exposure to INCB050465 will be summarized descriptively as the following:

- **Duration of treatment with INCB050465 (days):** Date of last dose of study drug date of first dose of study drug + 1.
- Duration of treatment with INCB050465 for initial QD schedule (days): Date of last dose of study drug during initial QD schedule date of first dose of study drug + 1.
- **Duration of treatment with INCB050465 for QW schedule (weeks):** Ceiling of [(date of last dose of INCB050465 during QW schedule date of first dose of INCB050465 during QW schedule + 1) / 7].
- Average reported daily dose of INCB050465 for initial QD schedule (mg/day): Total reported INCB050465 dose taken during initial QD schedule (mg) / duration of treatment with INCB050465 for initial QD schedule (days).

- Average reported weekly dose of INCB050465 for QW schedule (mg/week): Total reported INCB050465 dose taken during QW schedule (mg) / duration of treatment with INCB050465 for QW schedule (weeks).
- **INCB050465 dose modifications:** Number of subjects who had INCB050465 dose reduction and interruption will be summarized for initial QD schedule, QW schedule, and overall.

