8.2.2. Adverse Events of Special Interest or Adverse Events of Clinical Interest

Specific AEs, or groups of AEs, will be followed as part of standard safety monitoring activities.

- ALT \geq 5 × ULN
- AST \geq 5 × ULN
- Colitis
- Diarrhea > Grade 2
- Rash \geq Grade 2
- Intestinal perforation
- Pneumonitis
- Pneumocystis jirovecii infection
- CMV infection
- Herpes simplex virus infection
- Varicella zoster virus infection
- Exfoliative dermatitis

The number of subjects who experienced any TEAEs of special interest will be summarized by maximum severity. Time to onset of new or worsening Grade 3 or 4 AEs will be summarized for ALT, AST, neutropenia, colitis, intestinal perforation, pneumonitis, *Pneumocystis jirovecii* infection, CMV infection, herpes simplex virus infection, varicella zoster virus infection, and exfoliative dermatitis. For rash and diarrhea events, time to onset of new or worsening Grade 2 or higher AEs will be summarized. ALT, AST, and neutropenia will be summarized based on the laboratory data.

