8.2.3. Adverse Event Summaries

An overall summary of AEs will include:

- Number (%) of subjects reporting any TEAEs
- Number (%) of subjects reporting any SAEs
- Number (%) of subjects reporting any Grade 3 or 4 TEAEs
- Number (%) of subjects reporting any TEAEs related to INCB050465
- Number (%) of subjects reporting any SAEs related to INCB050465
- Number (%) of subjects reporting any Grade 3 or 4 AEs related to INCB050465
- Number (%) of subjects who temporarily interrupted INCB050465 because of TEAEs
- Number (%) of subjects who permanently discontinued INCB050465 because of TEAEs
- Number (%) of subjects with INCB050465 dose reductions because of TEAEs

- Number (%) of subjects who had a fatal TEAE
- Number (%) of subjects reporting any TEAEs during QW schedule
- Number (%) of subjects reporting any SAEs during QW schedule
- Number (%) of subjects reporting any Grade 3 or 4 TEAEs during QW schedule
- Number (%) of subjects reporting any TEAEs related to INCB050465 during QW schedule
- Number (%) of subjects who temporarily interrupted INCB050465 because of TEAEs during QW schedule
- Number (%) of subjects who permanently discontinued INCB050465 because of TEAEs during QW schedule
- Number (%) of subjects with INCB050465 dose reductions because of TEAEs during QW schedule
- Number (%) of subjects who had a fatal TEAE during QW schedule

The following summaries will be produced by MedDRA term (if 10 or fewer subjects appear in a table, a listing may be appropriate):

- Summary of TEAEs by SOC and PT
- Summary of TEAEs by PT in decreasing order of frequency
- Summary of TEAEs by SOC, PT, and maximum severity
- Summary of Grade 3 or 4 TEAEs by SOC and PT
- Summary of INCB050465 treatment-related AEs by SOC and PT
- Summary of INCB050465 treatment-related AEs by SOC, PT, and maximum severity
- Summary of Grade 3 or 4 INCB050465 treatment-related AEs by SOC and PT
- Summary of TEAEs leading to death by SOC and PT
- Summary of treatment-emergent SAEs by SOC and PT
- Summary of treatment-emergent SAEs by PT in decreasing order of frequency
- Summary of INCB050465 treatment-related SAEs by SOC and PT
- Summary of TEAEs leading to INCB050465 dose reduction by SOC and PT
- Summary of TEAEs leading to INCB050465 dose interruption by SOC and PT
- Summary of TEAEs leading to discontinuation of INCB050465 by SOC and PT
- Summary of TEAEs during QW schedule by SOC and PT
- Summary of Grade 3 or 4 TEAEs during QW schedule by SOC and PT

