3.2.2	Summary of Treatment-Emergent Adverse Events by MedDRA System Organ Class and Preferred Term	Safety	X	X
3.2.3	Summary of Treatment-Emergent Adverse Events by MedDRA Preferred Term in Decreasing Order of Frequency			X
3.2.4	Summary of Treatment-Emergent Adverse Events by MedDRA System Organ Class, Preferred Term, and Maximum Severity	Safety X		
3.2.5	Summary of Grade 3 or 4 Treatment-Emergent Adverse Events by MedDRA System Organ Class and Preferred Term	Safety	Safety X X	
3.2.6	Summary of INCB050465 Treatment-Related Adverse Events by MedDRA System Organ Class and Preferred Term	Safety	X	
3.2.7	Summary of INCB050465 Treatment-Related Adverse Events by MedDRA System Organ Class, Preferred Term, and Maximum Severity	Safety	X	
3.2.8	Summary of Grade 3 or 4 INCB050465 Treatment-Related Adverse Events by MedDRA System Organ Class and Preferred Term	Safety	X	
3.2.9	Summary of Treatment-Emergent Adverse Events With a Fatal Outcome by MedDRA System Organ Class and Preferred Term	Safety	X	X
3.2.10	Summary of Serious Treatment-Emergent Adverse Events by MedDRA System Organ Class and Preferred Term	Safety	X	X
3.2.11	Summary of Serious Treatment-Emergent Adverse Events by Preferred Term in Decreasing Order of Frequency	Safety	X	X
3.2.12	Summary of INCB050465 Treatment-Related Serious Adverse Events by MedDRA System Organ Class and Preferred Term	Safety	X	X
3.2.13	Summary of Treatment-Emergent Adverse Events Leading to INCB050465 Dose Reduction by MedDRA System Organ Class and Preferred Term	Safety	X	
3.2.14	Summary of Treatment-Emergent Adverse Events Leading to INCB050465 Dose Interruption by MedDRA System Organ Class and Preferred Term	Safety	X	
3.2.15	Summary of Treatment-Emergent Adverse Events Leading to Discontinuation of INCB050465 by MedDRA System Organ Class and Preferred Term	Safety	X	X
3.2.16	Summary of Selected Treatment-Emergent Adverse Events of Special Interest by Highest Grade	Safety		X
3.2.17	Summary of Time to Onset of Selected Treatment-Emergent Adverse Events of Special Interest	Safety		X
3.2.18	Summary of Treatment-Emergent Adverse Events During QW Schedule by MedDRA System Organ Class and Preferred Term	Safety	X	X

Table No.	Title	Population	Standard	In-Text
3.2.19	Summary of Grade 3 or 4 Treatment-Emergent Adverse Events During QW Schedule by MedDRA System Organ Class and Preferred Term	Safety	X	X
3.2.20	Summary of INCB050465 Treatment-Related Adverse Events During QW Schedule by MedDRA System Organ Class and Preferred Term	Safety	X	

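### Adverse events are summarised for the weekly phase but not the daily phase, with no weekly-phase at-risk denominator, so toxicity is not described by schedule on a comparable basis

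*SAP*

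**What the plan says.** Protocol 1.4 gives the reason for the schedule change: "This once-weekly regimen is proposed to maintain response while providing time off from pathway inhibition, which may reduce the frequency of AEs". It rests on the earlier phase 1/2 study, where 11 of 46 subjects (24%) stopped treatment because of an adverse event.

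SAP 8.2.3 lists whole-study rows for the overall summary and then eight rows restricted to the weekly phase, starting with "Number (%) of subjects reporting any TEAEs during QW schedule". Appendix A adds nine weekly-phase tables, 3.2.18 to 3.2.26, of which the first is "Summary of Treatment-Emergent Adverse Events During QW Schedule by MedDRA System Organ Class and Preferred Term". Neither place has a row or table for the daily phase. Appendix A lists the safety population for these tables, and SAP 5.3.3 defines that as everyone with at least one dose.

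For events of special interest, SAP 8.2.2 says "The number of subjects who experienced any TEAEs of special interest will be summarized by maximum severity". The matching Table 3.2.16 is "Summary of Selected Treatment-Emergent Adverse Events of Special Interest by Highest Grade". A separate Table 3.2.17 is "Summary of Time to Onset of Selected Treatment-Emergent Adverse Events of Special Interest". Neither title mentions schedule.

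SAP 6.4 does treat the phases separately. It derives "Duration of treatment with INCB050465 for initial QD schedule (days"), a corresponding QW duration in weeks, and dose reductions and interruptions for QD, QW and overall.

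**The concern.** The weekly phase was introduced with tolerability in mind and the SAP gives it nine tables of its own, so readers will look for the daily-phase figure. Three things stand in the way.

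- **The daily figure is missing and cannot be recovered from the tables.** A subject with the same event in both phases counts once overall, so overall minus QW gives only a lower bound.
- **The phases differ in length.** The daily phase is planned at 8 weeks; the weekly phase is open-ended. A crude percentage grows with time at risk.
- **The listed denominator includes subjects who were never at risk.** Anyone who stops during daily dosing dilutes the QW percentage.

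Table 3.2.16 covers colitis, diarrhea, pneumonitis, rash and exfoliative dermatitis, all of which Protocol 1.3 names among the events behind discontinuations in the earlier study. Their phase matters most, and that table does not show it. What is at stake is the clarity of the safety description, not the primary endpoint.

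**Working it through.** **The plan's own figure.** Protocol 1.4: 11/46 = 23.9%, which rounds to the stated 24%. Among responders, 7/20 = 35%, as stated.

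**Count of planned outputs (SAP 8.2.3, Appendix A).**
- Overall-summary rows: 8 for QW, 0 for QD.
- Tables by system organ class and preferred term: 9 for QW (3.2.18 to 3.2.26), 0 for QD.
- Special-interest tables split by schedule: 0 of 2.
- Rates per unit of person-time: 0.

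**Why subtraction fails.** If N subjects have an event overall and M have it during QW, the QD count lies between N − M and N. With assumed counts N = 40 and M = 30, that is 10 to 40.

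**Phase lengths.** QD is 8 weeks = 56 days (Protocol Table 3). The Synopsis expects treatment to last while the subject "has not met withdrawal criteria (approximately 9 months"), taken here as 274 days. QW is then 274 − 56 = 218 days, and 218/56 = 3.9. At the earlier study's median treatment duration of 104 days (Protocol 1.3), QW is 104 − 56 = 48 days, and 48/56 = 0.86.

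**Effect on crude percentages.** Assume a constant hazard h per day, so that P(event in phase) = 1 − exp(−h × days). The rates are assumptions; the documents hold no event counts.

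| Rate per 100 person-days (QD) | QD, 56 days | QW, 218 days, same rate | QW, 218 days, rate halved | QW, 48 days, same rate |
|---|---|---|---|---|
| 0.1 | 5.4% | 19.6% | 10.3% | 4.7% |
| 0.2 | 10.6% | 35.3% | 19.6% | 9.2% |
| 0.4 | 20.1% | 58.2% | 35.3% | 17.5% |

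With a long weekly phase, a halved rate still gives the higher crude figure. With a short one, equal rates look slightly favourable to QW.

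**Effect of the denominator.** Assume exponential time on treatment. The share reaching day 56 is exp(−56 × ln 2/104) = 69% with a 104-day median, and exp(−56/274) = 82% with a 274-day mean. A QW percentage on the safety population is then 31% or 18% lower, in relative terms, than one on subjects who started QW. For example, with the 104-day median and 0.2 events per 100 person-days in both phases, QW incidence is 15.9% on the safety population and 23.1% on QW starters.

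**What a person-time rate would do.** Under constant hazard it returns the true QW:QD ratios, 1.0 and 0.5.

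**What it would not do.** Suppose the hazard under daily dosing is 0.01 per week in the first 8 weeks and would be 0.04 afterwards, and weekly dosing halves the later value to 0.02. The rates read 1 per 100 subject-weeks (QD) and 2 per 100 (QW). A real halving looks like a doubling even with the correct time base.

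**The case against.** The strongest objection is that the limit lies in the design. Every subject receives daily then weekly dosing in a fixed order, with no concurrent daily arm. Protocol 4.2 plans no comparison between subjects or with historical controls, and the safety objective is only to characterize safety. In the earlier study all but one of the events leading to discontinuation came after the 9-week assessment, and Protocol 5.4.3 says most immune-related events occur after 9 weeks. The daily phase is therefore the expected low-event window. Protocol Table 3 also lets a first dose reduction move a subject from daily to weekly dosing early, so entry to QW can depend on toxicity. All of this stands. A reader might infer that the missing tables are why the trial cannot show that weekly dosing lowered toxicity; the documents do not support that, because no table could show it here.

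A reader might also infer that the plan ignores time at risk. That is too broad. SAP 6.4 summarises duration by schedule and splits dose modifications both ways, and Table 3.2.17 gives onset times for special-interest events. What is missing is exposure as the denominator for adverse events. Nor are those events invisible by phase: individual preferred terms would appear in the QW tables, and Listings 2.7.1 and 2.7.2 hold dosing and event data from which rates could be derived later.

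The numerical illustration depends on assumed rates and its direction reverses with a short weekly phase, so it does not support saying that QW will always look worse. Finally, Appendix A calls its lists a guideline, and the shells, kept separately, may set a different denominator.

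None of this supplies a daily-phase summary or a stated at-risk set for QW. Fixing both in advance is better than deriving them after the data are seen.

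**Conclusion.** The point holds as a gap in description. The planned tables give crude adverse-event percentages for the whole study and for QW, no QD counterpart, no schedule split of Table 3.2.16, and no denominator limited to subjects or time at risk.

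The size cannot be estimated from the documents. Under the assumed constant hazards, equal underlying rates give QW:QD crude ratios from about 0.9 (104 days) to between 2.9 and 3.6 (274 days). Under exponential time on treatment, the safety-population denominator lowers QW percentages by 18% to 31% in relative terms. The table counts and the subtraction argument need no such assumptions.

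The primary endpoint, the futility rule and the error rates are not affected. The change is worth making because it uses data already collected, but it would not support a causal statement about weekly dosing.

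**What to change.** 1. In Table 3.2.1 and Tables 3.2.18 to 3.2.26, add an initial-QD column beside QW. Split Table 3.2.16 by schedule.
2. Use subjects who received at least one QW dose as the denominator for QW percentages.
3. For each phase, show subjects with a first event in that phase per 100 subject-weeks at risk. Count subjects rather than event records, because Protocol 8.1.2 records each change in severity as a separate event.
4. Assign events to a phase by date of onset or worsening.
5. Match the at-risk window to the collection window. The SAP 6.4 durations stop at the last dose, while Protocol 8.1.2 collects new events for at least 30 days afterwards. End the window at implementation of Amendment 4 for events that Protocol 7.4.1 no longer requires to be recorded.
6. Keep the presentation descriptive. Footnote that schedule is confounded with time on study, with selection of who remains on drug, and with early entry to weekly dosing through dose reduction, so the columns cannot show that weekly dosing lowered toxicity.
7. In the QW list of SAP 8.2.3, the treatment-related serious event line lacks the QW qualifier that Table 3.2.23 carries; align the two.

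Cost: wording in SAP 8.2 and the shells, and modest programming. No new data are needed. The downside is a side-by-side display that invites comparison and must carry the footnote.
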